2.3 Participants disposition, demographics and other baseline characteristics

2.3.1 Participants disposition

Participant's disposition will be assessed at screening, at end of treatment and at end of study.

The number of participants screened will be presented. In addition, the reasons for screen failures will be provided.

The number and percentage of participants in the SAF who completed double-blind study drug and who discontinued from double-blind study drug prematurely (including the reason for discontinuation) will be summarized.

The number and percentage of participants in the FAS who completed study and who discontinued from study prematurely (including the reason for discontinuation) will be summarized.

For each protocol deviation (PD), the number and percentage of participants for whom the PD applies will be tabulated. Summary by protocol deviation category will be provided in addition to summary by protocol deviation category and deviation term.

2.3.2 Background and demographic characteristics

Participant demographic and baseline characteristics will include:

- Age
- Age categories (≤ 65 , > 65 years)
- Sex
- Race
- Ethnicity
- Height
- Weight

[figure not shown]
- BMI

Background disease characteristics will include:

- Oxygen saturation at baseline ($\leq 94\%$; $> 94\%$)
- Requiring supplemental oxygen at baseline (No/Yes)
- Supplemental Oxygen Flow rate (L/min) (see also [section 2.4.2.3](#))
- Number of days from onset of symptoms to first dose of study drug
- Number days from hospital admission to first dose of study drug
- Chest imaging (x-ray or CT scan) status at baseline (Normal/Abnormal/not available)
- Pre-morbid oxygen requirement (No/Yes)
- 
- Tachypnea (i.e. respiratory rate > 24 bpm) at baseline (No/Yes)

Comorbidities will include:

- Number of comorbidities (0,1 >1) , where comorbidities include the following list of solicited terms: Cerebrovascular disease, Chronic heart disease, Hypertension, Asthma, COPD, Chronic kidney disease, Malignant neoplasm, Diabetes.

Demographic and other baseline data will be summarized descriptively by treatment group for all study participants in the FAS.

Categorical data will be presented as frequencies and percentages. For continuous data, mean, standard deviation, median, minimum, and maximum will be presented. For selected parameters, 25th and 75th percentiles will also be presented.

2.3.3 Medical history and current medical condition

Any medical history, including protocol-solicited medical history and current medical conditions will be coded using the Medical Dictionary for Regulatory Activities (MedDra).

As indicated in [section 2.3.2](#), number and percentages of comorbidities will be analyzed.

2.4 Treatments (study treatment, rescue medication, concomitant therapies, compliance)

2.4.1 Study treatment / compliance

Duration of exposure to double-blind study drug will be defined as time from first dose of treatment to last dose of study drug.

The analysis of exposure to double-blind study drug will be based on the SAF. The duration of exposure to study treatment will be summarized by component of study treatment (i.e. HCQ/Placebo and AZI/Placebo). The number and percentage of participants by cumulative exposure levels (e.g. ≥ 1 day; ≥ 2 days; ≥ 5 days; ≥ 8 days; 10 days) will also be reported.

2.4.2 Prior, concomitant and post therapies

Analyses described in this section will be performed on the safety set.

2.4.2.1 Concomitant medication

Records on the Prior and Concomitant Medications eCRF page will be coded using the WHO drug dictionary. All medications will be classified as prior or concomitant medication as follows:

- Prior medications are defined as drugs taken and stopped prior to start of the study medication on Day 1.
- Concomitant medications are defined as drugs taken at least once after the start of the study medication on Day 1

Medications will be categorized into one (and only one) of the two classes based on recorded or imputed start and end dates. When incomplete or missing, dates will be imputed according to Novartis standards ([Section 5.1.3](#)).

Concomitant medications will be summarized by treatment group, drug class (ATC level 1) and preferred term.

2.4.2.2 Surgical and medical procedures

Records on the surgical and medical procedures eCRF page will be coded using the MedDRA dictionary. All procedures will be classified as prior or concomitant procedure, in the same way as done for concomitant medications.

Imputation rules for start and end dates will follow the same rule as for the concomitant medications ([Section 5.1.4](#)).

Analysis of medical procedures that are specific to the Covid-19 indication are covered in [Section 2.7](#) of this SAP. Imputation rules describes in [Section 5.1.4](#) should not apply in this case. Other surgical and medical procedures will not be summarized.

2.4.2.3 Supplemental oxygen therapy

Supplemental oxygen therapy was solicited at the Screening, Day 1, Day 2, Day 4, Day 6, Day 8, Early Discharge/Day 10, at follow-up Day 15 visit and at EOS/Day 40. This assessment included a measure of Oxygen Flow rate in L/min.

Oxygen flow rate (L/min) at baseline will be analyzed using descriptive summary statistics. For patient who did not receive supplemental oxygen therapy at baseline, Oxygen Flow rate (L/m) will derived as 0. This parameter will be reported along with other background disease characteristics (see [section 2.3.2](#)).

2.5 Analysis of the primary objective

The primary objective of the study is to demonstrate in participants receiving best standard of care that the percentage who achieve clinical response with hydroxychloroquine or hydroxychloroquine plus azithromycin is superior to placebo by Day 15.

2.5.1 Definition of the primary estimand

The primary clinical question of interest is: What is the effect of hydroxychloroquine and hydroxychloroquine plus azithromycin versus placebo on the percentage of participants achieving clinical response by Day 15 in participants with moderate to severe COVID-19 disease who are receiving standard of care?

The primary estimand is described by the following attributes:

Population: Adults at least 18 years of age, with SARS-COV-2 confirmed by PCR or rapid test ≤ 4 days prior to randomization who are currently hospitalized or who require hospitalization for COVID-19 disease. The primary efficacy analysis will be based on the Full analysis set (FAS), following the intention-to-treat principle.

[figure not shown]
Endpoint: clinical response by Day 15. For participants *with a pre-morbid oxygen* requirement, clinical response is defined as: discharge (or ready to discharge as evidenced by normal body temperature and respiratory rate, and stable oxygen saturation on ambient air or $\leq 2L$ supplemental oxygen) OR survival without need for mechanical ventilation. For participants *without a pre-morbid oxygen* requirement, clinical response is defined as: discharge (or ready for discharge) OR survival without need for mechanical ventilation or oxygen supplementation for the last 24 hours.

Treatment of interest: The randomized treatment (hydroxychloroquine or hydroxychloroquine plus azithromycin or placebo) added to concomitant standard of care treatments used to treat moderate-severe COVID-19 disease.

Intercurrent events: Based on the definition of the endpoint there are no intercurrent events which need to be accounted for outside of the treatment of interest attribute of the estimand.

Summary measure: Odds-ratio comparing experimental treatments of interest to placebo.

[REDACTED]

2.5.2 Statistical hypothesis, model, and method of analysis

The number (%) of participants who achieved clinical response will be summarized by Day 15 will be summarized. Analysis will be performed on the FAS.

2.5.3 Handling of remaining intercurrent events of primary estimand

The primary analysis has incorporated all potential intercurrent events related to treatment or concomitant therapy as part of the treatment of interest attribute of the estimand and no other intercurrent events are necessary.

2.5.4 Handling of missing values not related to intercurrent event

Given that the participants in this clinical trial will be hospitalized for their participation, it is not expected that there will be any additional missing data in the primary analysis.

Consideration with regards to handling death was provided in the derivation of the components of the clinical response.

In case of premature discontinuation from study, ongoing/missing end date of pulmonary support will not be imputed, i.e. pulmonary support should not be considered ended in this case.

2.5.5 Sensitivity analysis for the primary estimand

No sensitivity analysis are planned.

2.5.6 Supplementary analysis

No supplementary analysis are planned.

2.5.7 Supportive analyses

Clinical response by Day 28.

The number (%) of participants who achieved clinical response by Day 28 will be summarized by Day 28. Analysis will be performed on the FAS.

2.6 Analysis of the secondary objectives controlled for multiplicity

2.6.1 Secondary endpoint controlled for multiplicity

The secondary efficacy endpoint of the percentage of participants with negative or below LLOQ - SARS-COV-2 based on PCR by Day 10 will determined based on the PCR test that is performed at Day 6 and Day 10/Day of discharge. Data available in the literature would indicate that when viral clearance is achieved, participants will not reverse their viral clearance during the 15-day period.

2.6.2 Statistical hypothesis, model, and method of analysis

The number (%) of participants who achieved viral clearance by Day 6 and by Day 10 will be summarized. Analysis will be performed on the FAS.

2.6.3 Handling of missing values/censoring/discontinuations

Viral clearance will be based on available PCR results by Day 10, which means that the last available PCR results available at Day 10 or an earlier visit will be used to determine viral clearance status. Patients who do not have PCR results post first dose of treatment will be considered as not having reached viral clearance.

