2.2 Secondary estimands

The clinical question of interest is: What is the effect of the hydroxychloroquine and hydroxychloroquine plus azithromycin versus placebo on the presence or absence of virus which will be represented by the percentage of participants achieving viral clearance by Day 15 in participants with moderate to severe COVID-19 disease who are receiving standard of care?

The justification for the secondary estimand is that it will capture both the effect of the study treatments and the effect of any standard of care treatments, dosed as required at the time of randomization, mirroring the conditions in clinical practice. Further details can be found in [Section 12](#).

The secondary estimand is described by the following attributes:

Population: Adults at least 18 years of age, with SARS-COV-2 confirmed by PCR or rapid test ≤ 4 days prior to randomization who are currently hospitalized or who require hospitalization for COVID-19 disease. Further details about the population are provided in [Section 5](#).

Endpoint: The percentage of participants with negative or below LLOQ - SARS-COV-2 based on PCR by Day 15

Treatment of interest: the randomized treatment (hydroxychloroquine or hydroxychloroquine plus azithromycin or placebo) added to concomitant standard of care, used to treat moderate-severe COVID-19 disease. Further details about the investigational treatment and control treatment are provided in [Section 6](#).

Handling of remaining intercurrent events will be considered as treatment failures (Composite strategy):

- Death

[figure not shown]
The summary measure: Odds-ratio comparing experimental treatments of interest to placebo

3 Study design

This study is a multi-center, randomized, blinded, three-arm parallel-group, placebo-controlled trial to evaluate the safety and efficacy of hydroxychloroquine monotherapy or in combination with azithromycin in participants with moderate and severe COVID-19 disease.

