8.3 Efficacy

8.3.1 COVID-19 Participant status

The following details on the participants' status will be collected in the at Baseline and hospital discharge at a minimum, in addition any change in status must be reported in the CRF:

- Hospitalization (including dates of admission and discharge* or ready for discharge)
- ICU stay (including dates of admission** and discharge***)
- Pre-morbid supplemental oxygen requirements and its volume if yes (start and stop dates, volume: L)
- Mechanical ventilation requirements (start and stop dates)
- Participant survival status (i.e. death)

[REDACTED]

* If a participant is unable to be discharged due to administrative reasons, then the date that the participant, in the opinion of the investigator, is ready to be discharged (i.e. ready for discharge as evidenced by normal body temperature and respiratory rate, and stable oxygen saturation on ambient air or $\leq 2L$ supplemental oxygen) should be reported in the hospitalization status for date of discharge.

** In the case that a participant cannot be admitted to the ICU, even if the participant's condition is severe enough in the opinion of the investigator (e.g. due to administrative reasons under the current circumstances), this is also considered under admission and date of ICU admission should be reported

***If a participant is unable to be discharged from ICU due to administrative reasons, then the date that the participant, in the opinion of the investigator, is ready to be discharged should be reported in the ICU status for date of discharge.

[REDACTED]

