1.1 Study design

This study is a multi-center, randomized, double-blind, three-arm parallel-group, placebo-controlled trial to evaluate the safety and efficacy of hydroxychloroquine monotherapy or in combination with azithromycin in participants with moderate and severe COVID-19 disease. The study will include: a screening period of up to four days to obtain the informed consent and assess participant's eligibility; a treatment period of 10 days; and an observation period of an additional 30 days (until Day 40) with Day 40 being the end of study visit. All participants are expected to be treated with available standard of care (SoC) therapy for COVID-19 disease throughout the study ([Figure 1-1](#)).

Approximately 444 participants were to be randomized into either of three arms with a 1:1:1 ratio. When the decision was made to halt the study, a total of 20 participants had been randomized (including one mis-randomized participant).

[figure not shown]
Study will be conducted in the United States.

No formal interim analysis is planned for this trial.

The CSR will be finalized after the final database lock, once the 20 randomized participants have completed Day 40 or discontinued study prior to Day 40.

Considering the limited number of participants randomized, only serious adverse events were reviewed during safety monitoring using a data monitoring committee (DMC).

Figure 1-1 Study design

All participants will be treated with the best available standard of care for COVID-19 disease throughout the study

¹ The total treatment duration of hydroxychloroquine will be 10 days. The total treatment duration of azithromycin will be 5 days. In case a participant is discharged before the end of treatment period (Day 10) he/she may continue study medication at home until Day 10 if QTcF \leq 480 ms at the time of discharge based on the local ECG data. Otherwise, treatment will be discontinued at the time of discharge (before Day 10).

² The loading dose of AZI/matching placebo (Day 1) should be taken 4 hours after loading dose of HCQ/matching placebo

³ After HCQ/matching placebo loading dose on Day 1, the following HCQ/matching placebo doses as a maintenance therapy should be initiated within approximately 8 hours (not to exceed 12 hours).

HCQ: hydroxychloroquine, AZI: azithromycin, o.d.: once a day, t.i.d: three times a day

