2.8.2 Deaths

The primary causes of death may be attributable to complication of COVID-19 disease or any other reasons.

Deaths will be listed.

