3.2 Secondary endpoint

Data available from recent studies published by [Gautret et al., 2020](#) would indicate that viral clearance for hydroxychloroquine plus azithromycin is high. In one study, all participants receiving this combination therapy achieved viral clearance by Day 6. Participants receiving standard of care generally do not achieve a response rate higher than 50%. However, many of these studies are small and often not randomized. If one were to assume that hydroxychloroquine plus azithromycin has an 80% response rate by Day 15 and standard of care has a 50% response rate by Day 15, under this scenario, using the sample size justified for the primary efficacy endpoint, the 30% treatment difference corresponds to an odds-ratio of 4.0 and given 148 participants per treatment group. There will be more than 99% power to detect such a treatment difference.

4 Change to protocol specified analyses

None.

5 Appendix

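### SAP 2.6.3 omits the protocol's rule that death is a failure for viral clearance, and SAP Section 4 wrongly reports no changes to the protocol analyses (minor; descriptive output only)

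*SAP*

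**What the plan says.** **Death and viral clearance.** Protocol 2.2 states "Handling of remaining intercurrent events will be considered as treatment failures (Composite strategy", and the event listed beneath is death. SAP 2.6.1 bases clearance on the "PCR test that is performed at Day 6 and Day 10/Day of discharge". SAP 2.6.2 says that the number and percentage of "participants who achieved viral clearance by Day 6 and by Day 10 will be summarized", on the FAS. For status, SAP 2.6.3 says that "the last available PCR results available at Day 10 or an earlier visit will be used to determine viral clearance status"; a participant with no post-dose PCR counts as not cleared. Death is not mentioned there. SAP 2.5.4 refers to death only for the components of clinical response. SAP 2.8.2 adds "Deaths will be listed".

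**Changes from the protocol.** SAP Section 4, headed "Change to protocol specified analyses", contains the single word None. The SAP Introduction says that the trial was halted on 19 June 2020, that only an abbreviated report will follow, and that the analyses in the previous SAP were cut back. It itemises nothing.

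**Oxygen endpoint.** SAP Table 1-1 restricts time to return to pre-morbid oxygen requirement to participants on supplemental oxygen at randomization. SAP 2.7.1 names only the FAS.

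**Size of the trial.** SAP 1.1 reports that "a total of 20 participants had been randomized (including one mis-randomized participant" when the study was halted.

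**The concern.** The SAP Introduction says that the study report will be produced from this SAP, so programmers will follow 2.6.3. That section is explicit about participants without a post-dose PCR, and 2.5.4 is explicit about death for a different endpoint. Silence on death in 2.6.3 is therefore likely to be programmed as no rule. A participant who died with a negative last swab would be reported as a virological success, against the protocol's composite strategy. The death listing would show the death, but the percentage would still count it as cleared.

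Section 4 is where a reader looks for differences from the protocol. Its entry is wrong, and not every difference is announced elsewhere. The loss of closed testing, for example, has to be inferred from the absence of models, and the dropped subgroup and Standardized MedDRA Query (SMQ) summaries show only when the two documents are compared.

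For the oxygen endpoint, a full-FAS denominator would let participants who were not on oxygen at randomization count as returned without having recovered anything.

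**Working it through.** **1. The plan's own figures.** With 148 per arm, 60% against 40%, two-sided alpha 0.05 and a pooled normal approximation (Protocol 12.8.1, SAP 3.1):

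power = Φ{[0.20 − 1.96·√(2·0.5·0.5/148)] / √[(0.24 + 0.24)/148]} = Φ{(0.20 − 1.96·0.05812)/0.05695} = Φ(1.511) = 93.5%, against 93% stated.

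For clearance at 80% against 50%, the odds ratio is (0.8·0.5)/(0.2·0.5) = 4.0 and power is 99.99%, against more than 99% stated. The figures reproduce. Nothing below changes them, because SAP 5.4 implements no model.

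**2. The two death rules, for a participant who dies by the analysis day.**

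| Last post-dose PCR | Protocol 2.2 | SAP 2.6.3 as written |
|---|---|---|
| Positive | Failure | Not cleared |
| None | Failure | Not cleared |
| Negative | Failure | **Cleared** |

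Only the last row differs. An example is a negative Day 6 swab followed by death on Day 8. Scheduled post-dose swabs fall only at Day 6 and at Day 10 or discharge, so few participants can reach that row.

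**3. Size.** The FAS excludes mis-randomized participants (SAP 2.2), so it holds at most 20 − 1 = 19. One case moves a pooled percentage by 1/19 = 5.3 points. A by-arm percentage would move more, but the documents give no arm sizes. They also do not say whether any such death occurred.

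**4. Section 4 against the protocol.** These differences are visible in the text:

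| Protocol | SAP |
|---|---|
| Clearance by Day 15 (2.2, 12.5) | By Day 10, also Day 6 (Table 1-1, 2.6) |
| Logistic models and odds ratios, with response differences and 95% intervals for the primary endpoint (12.4.2, 12.5) | Counts only (2.5.2, 2.6.2, 5.4) |
| Closed testing of four hypotheses (12.5) | Absent |
| Non-parametric sensitivity analysis (12.4.5) | None (2.5.5) |
| Three subgroup factors (12.4.7) | Absent; Day 28 response added (2.5.7) |
| Kaplan-Meier for three endpoints (12.5) | Counts by Day 15 and Day 28 for two (2.7.1); negativity only as clearance by Day 6 and Day 10 |
| No rule for missing PCR | Last-available and no-PCR rules added (2.6.3) |
| Biomarker summaries (12.5.2) | Not conducted (2.9) |
| Adverse events by SMQ (12.5.1) | Absent (2.8.1) |
| On-treatment window ends 30 days after last dose (12.5.1) | Data after treatment start, to cut-off dates (2.1.1.6, 2.8) |
| Baseline on FAS and safety set; durations to randomization; solicited history summarized (12.2) | FAS only; durations to first dose; comorbidity counts (2.3.2, 2.3.3) |
| Vital signs listed, flagged and summarized (12.5.1) | Change-from-baseline summaries (2.8.4.2) |
| Medications and non-drug therapies before and after treatment start (12.3) | Concomitant medications only; procedures not specific to COVID-19 not summarized (2.4.2) |

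Protocol Table 8-1 marks SARS-CoV-2 tests at screening, Day 1, Day 6, Day 10 and unscheduled visits, and none at Day 15. The move to Day 10 therefore follows the swab schedule, but it is still a change. Laboratory listings and shift tables are left out because SAP 2.8.3.1 is partly redacted.

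**5. Oxygen endpoint.** SAP 2.7.1 defines return as no mechanical ventilation for anyone and, for those without a pre-morbid requirement, no supplemental oxygen. A participant off oxygen at randomization can meet this from the start. The documents do not give the number on oxygen, so no size is assigned.

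**6. Stale text.** SAP 2.5.1 keeps the odds ratio as summary measure. The headings of 2.6 and 2.6.1 still claim multiplicity control. The Table 1-1 objective says Day 15 beside a Day 10 endpoint, and the rates in 3.2 are for Day 15.

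**The case against.** The trial stopped at 20 participants, the report is abbreviated, and the Introduction says openly that analyses were reduced. Several reductions are stated where they apply: no models (5.4), no sensitivity analysis (2.5.5), no biomarker analysis (2.9), other procedures not summarized (2.4.2.2), and the Day 10 time point (Table 1-1, 2.6). A reader might infer from Section 4 that the changes were concealed. The documents do not support that. What stands is that the general statement is made relative to the previous SAP rather than the protocol, lists nothing, and does not cover changes that are not reductions, such as Day 28 response or the new PCR rules.

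On death, it can be said that a missing-data section need not repeal a protocol estimand. That is fair as to intent, but the rule as written gives the wrong status in one identifiable case.

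Four other stronger readings fail:

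- **A fixed count of departures.** Any number depends on how items are split.
- **The single final report as a departure.** Protocol 4.4 and 12.7 plan a Day 15 analysis, while the opening of Protocol 12 places the analyses after Day 40. The protocol conflicts with itself, and SAP 1.1 agrees with one side.
- **A clear switch of population for the oxygen endpoint.** The protocol has the same tension: Table 2-1 gives the subset, and 12.1 puts all efficacy variables on the FAS. Naming the FAS does not by itself delete a subset in the endpoint definition. This is an unresolved conflict.
- **A material shift in the safety window.** Ten treatment days plus 30 is Day 40, the end of study, so the windows differ mainly for participants who stop treatment early.

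**Conclusion.** The point holds, at minor severity. SAP 2.6.3 does not carry over the protocol's death rule for viral clearance, and the Section 4 entry is incorrect. The consequence for clearance is 5.3 points on a pooled FAS rate per affected participant, assuming a FAS of 19, and zero if nobody died by the analysis day after a last negative swab. The oxygen denominator and the stale wording need reconciling, but neither can be sized from the documents.

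A reader might infer that the trial's inference or its clearance result is compromised. The documents do not support this: no hypothesis is tested, no type I error or power claim depends on these points, and no such death is reported in them.

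**What to change.** 1. **SAP 2.6.3.** Add: *Participants who die on or before the analysis day (Day 6 or Day 10) are counted as not cleared, whatever their last PCR result.* Note that the protocol's Day 15 window is shortened to Day 10, so deaths on Days 11 to 15 no longer enter.
2. **SAP Section 4.** Replace the entry with an itemised list that includes at least the differences tabulated above, giving the halt as the reason where it applies. The sponsor should check it for completeness, including the laboratory outputs; no fixed count is needed. Leave report timing off the list, or record that the protocol's own statements on timing conflict.
3. **SAP 2.7.1.** State the subset on oxygen at randomization as the denominator, or declare the move to the FAS as a change.
4. **Stale text.** Remove or annotate the odds ratio in 2.5.1 and the multiplicity wording in 2.6 and 2.6.1. Align the Table 1-1 objective with Day 10, and note that the rates in 3.2 were assumed for Day 15.

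The cost is SAP wording and one line of derivation code for the death rule. Protocol 8.3.1 already collects "Participant survival status (i.e. death" in the status data, so nothing new has to be gathered.
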